## 4.0 PARTICIPANT POPULATION

Study enrollment has been closed since 15 Oct 2008 and no new study participants will be enrolled. Approximately 1,700 centers participated in the study and enrollment included 41,451 MemoryGel participants and 1,039 saline participants. As of the last annual study report (dated Nov 2013), the follow-up rates through six years were 21.8% for MemoryGel participants and 15.0% for saline participants.

The postapproval study was originally designed with the following eligibility criteria:

### **Eligibility Criteria: MemoryGel Breast Implant Participants**

#### **Inclusion Criteria**

To be included in the study, each MemoryGel participant must be a woman who:

1. Is a candidate for breast augmentation with Mentor MemoryGel breast implants and is at least 22 years old (primary or revision) **OR** is a candidate for breast reconstruction (primary or revision) with Mentor MemoryGel breast implants
2. Signs an Acknowledgement of Informed Decision from the patient brochure
3. Signs an Informed Consent Form and an Authorization to Disclose Health Information and Release Medical Records
4. Completes the baseline questionnaire (as evidenced by the participant's signature on the last page of the questionnaire).
5. Agrees to authorize return of the device(s) to Mentor if the device is explanted
6. Agrees via Informed Consent to comply with study follow-up, including full participation in all follow-up questionnaires and responding to questionnaires in their entirety
7. Is a U.S. resident

#### **Exclusion Criteria**

Consistent with the labeling, a woman is not eligible to receive Mentor MemoryGel implants and enroll in the postapproval study if she meets any of the following exclusion criteria:

1. Has active infection anywhere in her body.
2. Has existing breast cancer or pre-cancer of the breast without adequate treatment for those conditions.
3. Is currently pregnant or nursing.

### **Eligibility Criteria: Saline Breast Implant Control Participants**

#### **Inclusion Criteria**

To be included in the study, each saline control participant must be a woman who:

1. Is a candidate for breast augmentation and is at least 18 years old (primary or revision) **OR** is a candidate for breast reconstruction (primary or revision) with saline breast implants.
2. Signs an Informed Consent Form and an Authorization to Disclose Health Information and Release Medical Records
3. Completes the baseline questionnaire (as evidenced by the participant's signature on the last page of the questionnaire).
4. Agrees to authorize return of the device(s) to Mentor if they are Mentor devices.
5. Agrees via Informed Consent to comply with study follow-up, including full participation in all follow-up questionnaires and responding to questionnaires in their entirety
6. Is a U.S. resident

---

 Breast augmentation includes primary breast augmentation to increase the breast size, as well as revision surgery to correct or improve the result of an original primary breast augmentation surgery.

 Breast reconstruction includes primary reconstruction to replace breast tissue that has been removed due to cancer or trauma or that has failed to develop properly due to a severe breast abnormality. Breast reconstruction includes revision surgery to correct or improve the result of an original primary breast reconstruction surgery.

**Exclusion Criteria**

A woman is not eligible to enroll in the postapproval study as a saline control participant if she meets any of the following exclusion criteria:

1. Has current or past, unilateral or bilateral, silicone breast implants
2. Has active infection anywhere in her body
3. Has existing breast cancer or pre-cancer of the breast without adequate treatment for those conditions
4. Is currently pregnant or nursing

**Documentation of Non-Enrollment**

There may be circumstances where a participant meets all of the eligibility criteria, but ends up not enrolling in the MemoryGel™ PAS. To understand why this may occur there are two forms to document these reasons:

1. Non-Enrollment Form
2. Non-Participation Form

**Non-Enrollment Form**

The Non-Enrollment Form is used when a patient has **begun the enrollment process** and decides not to enroll (due to diagnosis of excluded condition, personal reasons, etc.); or the physician believes that the patient should not be enrolled (e.g., due to an ongoing clinical diagnosis of depression or other mental health disorder).

**Non-Participation Form**

The Non-Participation Form should be used after a patient has been counseled and educated about their choices in seeking MemoryGel™ implants, has not begun the MGPAS enrollment process, and declines to participate in MemoryGel™ PAS.

## 5.0 POSTAPPROVAL STUDY EVALUATIONS

### PHYSICIAN AGREEMENT

As a condition to receiving Mentor's MemoryGel Silicone Gel-filled Breast Implants, surgeons were required to participate as a site in the postapproval study. Participating physicians were required to sign a Physician Agreement indicating that they would adhere to the MemoryGel™ PAS study protocol. As part of the Agreement, which will continue to apply under this protocol amendment, the physician committed to:

- confirm that any necessary IRB approval (national or local) has been obtained;
- review and become thoroughly familiar with the study protocol;
- answer all the participant's questions about her role in MemoryGel™ PAS;
- adhere to the study protocol;
- ensure that the surgeon's staff understands and will adhere to the study protocol;
- assist MemoryGel™ PAS participants in identifying an MRI facility with a dedicated breast coil and sufficiently strong magnets (at least 1.5 Tesla); and
- comply with Mentor's procedures regarding return of explanted MemoryGel devices.

The postapproval study Agreement originally included the following additional physician commitments that were specific to enrollment, office visits, and annual questionnaires:

- *counsel and educate women seeking MemoryGel™ implants about their choices, and encourage them to enroll in the MemoryGel™ PAS to assist Mentor Corporation to comply with post-approval conditions, and explain how their participation will contribute to furthering the scientific data collected on silicone breast implants, and counsel them about their voluntary participation in MemoryGel™ PAS;*
- *identify saline implant control implant participants according to the study protocol and randomization schedule and counsel them about their voluntary participation in MemoryGel™ PAS;*
- *ensure Informed Consent and Authorization to Disclose Health Information and Release Medical Records are completed prior to implantation of MemoryGel or saline implants;*

- ensure that all enrollment documents as required by the protocol, are sent promptly to the third party study entity identified on the Business Return Envelopes provided to the surgeon;
- complete an Operative form for each study participant and return the form promptly to the third party study entity on the Business Return Envelopes provided to the surgeon (control participants will receive standard of care, not recorded as part of this protocol.);
- see each MemoryGel participant at Year 1, a second time during Years 4-6, a third time during Years 9-10, and also for unscheduled/interim visits to record all local complications and reasons for reoperation, with or without removal, and reasons for removal (control participants will receive standard of care, not recorded as part of the study.);
- assist MemoryGel™ PAS participants in identifying a board-certified rheumatologist and/or neurologist as appropriate;
- provide ongoing encouragement and communication to participants regarding completion of annual questionnaires through 10 years

## STUDY EVALUATIONS

This protocol amendment includes the following evaluations:

Evaluation	Evaluator
Unscheduled/interim reporting of secondary procedures/reoperations*	Surgeon
*MemoryGel participants only	

Surgeon evaluations are being done to record reoperation procedure information and reasons for reoperation, with or without removal, for the MemoryGel participants only. These data were also recorded under the original protocol. A flow chart of the postapproval study process is depicted in Figures 1 and 2 (gray highlights show completed actions). All data will be forwarded to a third party study entity that will be responsible for administering the study database and analyzing the study data.

The postapproval study originally included the following evaluations:

[figure not shown]
Evaluation	Evaluator
Baseline questionnaire (preoperative)	Participant
Operative procedure	Surgeon
Follow-up questionnaire annually, 1-10 years	Participant
Unscheduled/interim reporting of key local complications and results of MRI evaluations	Participant*
Unscheduled/interim reporting of results from rheumatological or neurological referral evaluations	Participant
1 visit in Year 1	Surgeon*
1 visit in Years 4-6	Surgeon*
1 visit in Years 9-10	Surgeon*
Unscheduled/Interim visits	Surgeon*
Questionnaire at time of any participant discontinuation (when possible)	Participant**

\*MemoryGel participants only

[figure not shown]
\*\*In addition, the third party study entity will complete a Discontinuation Form documenting the date and reasons for discontinuation

Surgeon evaluations are being done to record all local complications (including reasons for reoperation, with or without removal, and reasons for removal) for the MemoryGel participants only. Because of the mobility and general good health of participants who will be receiving MemoryGel implants, Mentor will encourage the appropriate medical societies to host Internet-available listings of surgeons who are available to perform follow-up evaluations of any MemoryGel participant in the postapproval study. A flow chart of the postapproval study process is depicted in Figures 1 and 2. All participant and surgeon data will be forwarded to a third party study entity that will be responsible for administering the study database and analyzing the study data

**Figure 1**  
**PROTOCOL AMENDMENT 2 POST APPROVAL STUDY PROCESS FLOW CHART:**  
**MEMORYGEL PARTICIPANTS**

**Figure 2**  
**PROTOCOL AMENDMENT 2 POST APPROVAL STUDY PROCESS FLOW CHART:**  
**SALINE CONTROL PARTICIPANTS**

### **5.1 Participant Follow-up**

The study is currently in year 7 and follow-up will continue through 10 years or until the National Breast Implant Registry opens for data collection, whichever occurs first. At each follow-up contact, the following data will be collected:

- Updated participant and physician contact information
- Updated patient medical history
- Explantation and reoperation information
- Reasons for reoperation, with or without removal.

The surgeon/investigative site will submit the completed data collection forms via Internet or mail to a third party entity for entry into the study database

### **5.2 Explantation and Discontinuation**

In the event a participant indicates her intention to withdraw from the study, the reason for withdrawal will be recorded. The surgeon or a third party entity will complete the Discontinuation Form provided in Section 15.

For details on the postapproval study evaluations under the original study design, including baseline, operative procedure, participant follow-up (annually, 1 to 10 years), physician follow-up, and explantations and discontinuation, see the previous protocol version (Amendment 1).

## **6.0 RETURNED DEVICES**

Pursuant to Mentor's policies and procedures, explanted MemoryGel and Mentor saline breast implants should be returned to Mentor Product Evaluation regardless of the reason for explant. Consistent with the patient's return authorization granted at the outset of her study participation, surgeons should return the explant to Mentor, using a product return kit.

Please call [name] for instructions and shipping information for return of explanted devices.

Mentor will use a good faith effort to obtain MemoryGel explanted devices if it becomes aware that explantation has occurred and the surgeon has not returned the devices. Mentor's saline breast implants, if explanted, will be handled in accordance with current standard operating procedures.

Upon receipt of the returned explant, Mentor Product Evaluation will examine the device by conducting a comprehensive investigation including visual and physical testing of the explanted device to try to determine the cause of a complaint, if any, or the condition of the device in accordance with established procedures and protocols. These analyses will be part of separate postapproval retrieval stud(ies) and/or product evaluation activities, and will not be considered part of this study.

Mentor requests that any explanted devices be sent to Mentor Worldwide, Product Evaluation Department, [name] USA for examination and analysis.

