## 2.0 OBJECTIVES

This amended protocol will collect data on secondary procedures/reoperations. The issues to be addressed include the following:

- What are the Kaplan-Meier (KM) implant removal and reoperation rates over time?
- What are the reasons for reoperation over time?

The postapproval study was originally designed to address the issues identified in Table 1, which includes reoperation data as described above.

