### 3.0 DESIGN

This protocol amendment includes participant follow-up only. Study enrollment has been closed since 15 Oct 2008 and no new study participants will be enrolled. Data collection will only take place if a participant requires a secondary procedure/reoperation. There are no longer requirements for scheduled office visits or annual participant questionnaires. The study is currently in year 7 and follow-up will continue through 10 years or until the National Breast Implant Registry opens for data collection, whichever occurs first.

As in the original protocol, there will be no concurrent controls needed as a source of comparison for secondary procedures/reoperations (see local complications category in original study design Tables 1 and 2). Thus, saline implant participants will not have data collected under this amended protocol.

Mentor will employ third party study entities that will be responsible for the following: (1) collecting data from surgeons; (2) entering data into and administering the study database; (3) generating follow-up reports as well as datasets; (4) meeting with Mentor on a regular basis; and (5) analyzing the study data. Mentor will be responsible for: (1) IRB approval; (2) monitoring third party entities; (3) analyzing the study data; and (4) periodic reporting to FDA.

The postapproval study was originally designed as follows:

*MemoryGel™ PAS uses a current cohort design of the first 41,900 women receiving Mentor's MemoryGel implants, with 10 years of follow-up. It will include augmentation, reconstruction, and revision patients, each in their naturally occurring proportions at participating study sites.*

*For the purpose of assessing rheumatological and neurological signs and symptoms, there also will be 1,000 saline breast implant patients from the participating surgeons' practices who will serve as concurrent controls. Concurrent control participants will be enrolled by approximately 30 physicians who routinely use saline implants. These investigative sites will be selected with the objective of obtaining the desired number of controls in an appropriate time frame, e.g. roughly the same time frame as the recruitment of MemoryGel subjects. These sites are to enroll all saline subjects meeting the specified eligibility criteria until 1,000 controls are recruited into this study.*

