## **10.0 MEDICAL RECORDS**

The postapproval study was originally designed to address the issues identified in [Table 1 and](#), in certain circumstances (see protocol Amendment 1), medical records of MemoryGel participants were to be obtained to confirm information provided by the participant. Medical records will be not obtained under this amended protocol.

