#### Complications/Reoperations

The cumulative incidence of key local complications (explantation, and reoperation) for women with MemoryGel implants will be estimated based on physician evaluations for the MemoryGel participants using Kaplan-Meier methodology to estimate the time to the first occurrence of the complication or reoperation. Ninety-five percent confidence intervals will be computed. In addition, the relative frequency of reasons for reoperation will be computed.

Under the original protocol, the purpose of the inclusion of the saline participants was to serve as concurrent controls for assessing rheumatologic and neurologic signs. Rheumatological and neurological data will not be collected under this protocol amendment.

Mentor will generate the following final clinical study reports for submission to FDA:

- One final report at the end of the study phase conducted under Amendment 1, including data from beginning of the study through the end of the study phase under Amendment 1. The statistical analysis will be conducted as described in the original protocol (see below).
- One final report at the end of the study phase conducted under Amendment 2, including data from the execution of Amendment 2 to the end of the study. The statistical analysis will be conducted as described above.

The original analyses conducted to address each of the postapproval study's original objectives are identified below and correspond to issues outlined in Table 1:

*It is important to recognize that this study is observational. As a result, data from this study can be used only to establish association, not causality, and data should be evaluated within the context of the broader composite of literature relating to these issues. All of the analyses, except for the analyses of rheumatological and neurological signs and symptoms, will be based on the MemoryGel participants only.*

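### Nothing in the visible text reconciles explantations the sponsor learns of with the surgeon-filed forms that alone feed the removal rate, so removals without a form would be missed

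*Combined protocol and SAP*

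**What the plan says.** All references are to the combined protocol and SAP.

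- **Objective (Section 2.0).** The first of the two remaining questions is "What are the Kaplan-Meier (KM) implant removal and reoperation rates over time".
- **Trigger (Section 3.0).** "Data collection will only take place if a participant requires a secondary procedure/reoperation". Scheduled visits and annual questionnaires have ended (Sections 3.0 and 8.0).
- **Route into the database (Sections 5.1 and 9.0).** The surgeon or site submits a completed form to the third party entity.
- **Analysis (Section 11.1, Amendment 2 text).** Explantation and reoperation "will be estimated based on physician evaluations for the MemoryGel participants using Kaplan-Meier methodology", as time to first occurrence. "Ninety-five percent confidence intervals will be computed".
- **Medical records (Section 10.0).** "Medical records will be not obtained under this amended protocol".
- **Devices (Section 6.0).** Explants are to go to the sponsor's product evaluation department whatever the reason for removal. Participants authorized this at entry (Section 4.0, MemoryGel inclusion criterion 5), and it remains a physician commitment (Section 5.0). If the device has not come back, "Mentor will use a good faith effort to obtain MemoryGel explanted devices if it becomes aware that explantation has occurred". On the laboratory work, the section says "These analyses will be part of separate postapproval retrieval stud(ies) and/or product evaluation activities, and will not be considered part of this study".
- **Event reporting (Section 7.0).** The third party reports specified events to the sponsor, and device-reporting data go into the annual reports. No link to the Kaplan-Meier rate is described.

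**The concern.** The form and the device go to different recipients: the form to the third party entity, the device to the sponsor. One can arrive without the other. The sponsor may therefore know of a removal that the study database lacks, and the text describes no step that brings the two together.

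This matters more under Amendment 2 than before. Data arrive only when something happens, and the other sources that could expose an unfiled form have been withdrawn. A missing form cannot be told apart from no event. The resulting error goes one way, towards a lower removal rate for the sponsor's own device, and the confidence interval reflects sampling error only.

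Incomplete reporting is plausible in this study. Six-year follow-up was 21.8% for MemoryGel participants (Sections 1.0 and 4.0). One of the two criteria for the former non-compliance discontinuation, both of which had to be met, was that no surgeon's complication form had been filed in three years (Section 14.0). Section 14.0 also aims to collect as much reoperation data as possible, and Section 1.0 presents the amended study as a pilot for the national registry. How completely surgeons report is something such a pilot should be able to show.

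**Working it through.** **1. Is there a figure to reproduce?** No. The documents give no expected removal rate, precision target, device-return rate or form-filing rate. The sample size in Section 11.2 rests on scleroderma incidence and on signs and symptoms, not on removal. The check is therefore of the text, followed by an illustration.

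**2. What happens to one removal?**

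| Form filed | Sponsor learns of removal | Stated action | Enters the removal rate |
|---|---|---|---|
| Yes | Yes or no | Form entered (5.1, 9.0) | Yes |
| No | Yes, device returned | Device examined (6.0) | No route described |
| No | Yes, device not returned | Effort to obtain the device (6.0) | No route described |
| No | No | None possible | No |

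Rows two and three are the gap. Row four is also missed, and reconciliation cannot recover it.

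**3. Direction and size.** Let *p* be the true removal probability over the window and *s* the share of removals with no form. Section 11.1 gives no censoring rule, so two cases are shown. Both assume that missing forms are unrelated to time of removal.

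- (a) The woman stays in the risk set as if her implant were in place: observed rate = *p*(1 − *s*).
- (b) She leaves the risk set at the unrecorded removal: observed rate = 1 − (1 − *p*)^(1 − *s*).

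Each cell gives (a) / (b). Every *p* and *s* is assumed.

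| True *p* | *s* = 5% | *s* = 10% | *s* = 20% | *s* = 50% |
|---|---|---|---|---|
| 5% | 4.75 / 4.76% | 4.50 / 4.51% | 4.00 / 4.02% | 2.50 / 2.53% |
| 10% | 9.50 / 9.52% | 9.00 / 9.05% | 8.00 / 8.08% | 5.00 / 5.13% |
| 20% | 19.00 / 19.10% | 18.00 / 18.19% | 16.00 / 16.35% | 10.00 / 10.56% |

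In (a) the relative shortfall is exactly *s*. In (b) it is slightly less: at *p* = 20% and *s* = 50% it is 1 − 10.56/20 = 47.2%. If *s* = 0 there is no bias.

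**4. What reconciliation could recover.** Let *r* be the share of form-less removals known to the sponsor. If all of these are resolved, the missed share falls from *s* to *s*(1 − *r*). With assumed *p* = 10% and *s* = 20% in case (a):

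- *r* = 0: 10% × 0.80 = 8.0%
- *r* = 0.5: 10% × (1 − 0.20 × 0.5) = 9.0%
- *r* = 1: 10.0%

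The documents do not give *r* either.

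**5. Can the overlap of the two sources measure completeness?** Only with a caveat. Both/(both + return only) estimates the chance that a form is filed given that the device came back. A surgeon who complies with one duty is likely to comply with the other, so this probably exceeds the chance of a form across all removals.

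**The case against.** **A reader might infer that the protocol bars such removals from counting. It does not.** The clause "and will not be considered part of this study" has the device analyses as its subject, that is, the visual and physical testing. It does not exclude the fact of a removal. The text is silent on whether a known explantation prompts a form.

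**A reader might also infer that the sentence on retrieving devices shows the sponsor holding removals it ignores.** That sentence applies when the device has not come back, and the sponsor's knowledge could come from a filed form, in which case nothing is missed. The documents give no count of removals known to the sponsor but lacking a form.

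**The sources are not independent.** The participating physician owes both the form and the device. Sites that file nothing may return nothing, and a removal by a surgeon outside the study may miss both routes. The yield of reconciliation could be small.

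**Relevant material could not be seen.** Amendment 1, the sponsor's device-return procedures and the flow charts in Figures 1 and 2 were not available. Any of them could contain the step.

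**The narrowing was deliberate.** FDA agreed to the reduced scope (Section 1.0), and Section 7.0 does put device-reporting data in the annual reports.

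These points remove any claim of a prohibition or of a known undercount, and they limit what the fix can promise. They do not supply the missing link between known explantations and the removal rate. Inclusion in an annual report is not inclusion in the Kaplan-Meier estimate.

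**Conclusion.** The gap holds on the visible text. The removal rate depends on surgeon-filed forms alone, and no step checks them against explantations that the sponsor learns of. Any removal without a form lowers the estimate, by about the share missed in relative terms. The confidence interval does not cover this error.

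The size cannot be determined. The tabulated values rest on assumed true rates of 5% to 20% and assumed missing-form shares of 5% to 50%, with missingness unrelated to time. The effect is nil if every removal has a form. Reconciliation would recover only those form-less removals that reach the sponsor.

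This is a worthwhile, low-cost improvement to one of the two remaining rates. It is not evidence that known removals have been left out.

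**What to change.** **Sections 6.0 and 9.0.** At set intervals the sponsor sends the third party entity its list of returned or reported explanted MemoryGel devices. The third party matches the list to actively consented participants, within the access limits of Section 15.0, and asks the site for any missing reoperation form. If a step of this kind already exists in the device-return procedures, cite it in the protocol.

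**Section 11.1.**

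- Count form-confirmed removals at the explant date, including those whose form follows a query.
- Report the Kaplan-Meier removal rate with and without removals known only from a returned device. Flag any that have to use the return date, since that date adds timing error.
- Report the number of removals found by form only, by return only and by both. State that the sources are not independent and that their overlap probably overstates completeness.

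**Cost.** Modest matching and query work, plus short protocol text. Section 6.0 does not say that return records carry a participant identifier, and some returns may come from women outside the study, so some devices will stay unmatched. The removal rate may become somewhat less favourable. The sponsor's restricted access to participant names and data is preserved if the match runs through the third party.
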